**Aim2: Examine long-term benefit of daily home use of lower electrical stimulation (long-term benefit):** Eligible participants will be randomized (ratio: 1:1) to either active (active group, n=20) or sham (sham group, n=20) therapy group. After receiving education, both groups will receive a home-based electrical stimulation system (Tennant Biomodulator device) for daily use at home up to 4 weeks. The duration of each treatment session per day will be one hour. The active group will receive an active electrical stimulation device. The control group will receive an identical device but without active electrical stimulation output. Participants and physicians who are treating the wound would be blinded to the type of device assignment. The study coordinator will be aware of assignment (active device or sham device). Each unit will be coded with a unique identification number. At the last visit, the study coordinator will reveal their group allocation. Since participating patients will have moderate-to-severe peripheral sensory neuropathy, they will be unable to determine via “feeling” whether or not they were receiving electrical stimulation. Patients will visit the clinic on weekly basis up to 4 weeks for assessing outcomes. The primary outcomes include changes in speed of wound healing and changes in plantar sensation. Secondary outcomes include patients self-report outcomes (e.g., pain, sleep quality, and quality of life), changes in mobility (e.g. physical activities and gait), and adverse outcomes (e.g., infection, amputation, etc.). Skin perfusion will be assessed similar to the method described in the Aim 1. Plantar sensation will be assessed using vibratory

perception threshold. Balance will be assessed using wearable sensors (BalanSENS, Biosensics LLC, MA, USA), mobility will be assessed using wearable sensors (PAMSys, Biosensics LLC, MA, USA), sleep quality will be assessed using PSQI questionnaire, and quality of life will be assessed using PROMIS Global.

Our hypotheses are

*H2:* Weekly speed of wound healing would be higher in the active group compared to the shame group

*H3:* Plantar sensation is improving in the active group in response to active therapy.

*H4:* Patient-reported outcomes and other secondary outcomes will be improved in the active group.

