### **Sample size estimation:**

The estimated number of study subjects is 40. The sample size for the short-term effect (immediate changes in skin perfusion) was estimated to achieve 85% power when comparing to baseline values, using assumed rates of 50% and 10% improvement, respectively. A two-sided test of results in evaluable subjects (qualified for analyses of efficacy on immediate changes on skin perfusion) will provide the specified power at a 5% significance level. Sample size calculations resulted in a requirement for a total of 27 subjects. The sample size for long term benefit was estimated based on our previous study (Najafi et al, Diabetes Sci & Tech, 2017) in which effectiveness of daily use of electrical stimulation to improve balance was examined using a randomized controlled trial model. An effect size of greater than Cohen’s  $d=1.35$  was observed for improvement of mobility post plantar electrical stimulation intervention. In this study we will use a power of 80%, two –tailed t-test, and alpha level of 5% to observe a significant improvement in the intervention group receiving active stimulation compared to sham group (with nonfunctional stimulator), 18 subjects per group is required. Assuming a 10% drop out, the estimated sample size would be 20 subjects per arm. We recognize that this sample size may not be sufficient to validate all primary and secondary outcomes, but would be sufficient to estimate trend and estimate the sample size for follow up study. Upon approval of the sponsor, availability of budget, and based on initial results (first 20 subjects), the sample size may be increased as well.

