### **Statistical analysis:**

Continuous variables are expressed as mean +/- standard deviation (SD). Unpaired t-tests, Mann-Whitney U-tests, and Chi-square-tests will be used for baseline comparison according to the scale of the investigated variable and the distribution of the data. Repeated measures ANOVA tests will be used for examining the effect of intervention in each group after adjusting by age and BMI. Similar test will be used for short-term effect (i.e. changes in skin perfusion immediately after electrical stimulation) and long term benefit (i.e. changes in primary and secondary outcomes after 4 weeks). To account for missing data (prevent entire subject data removal due to lack of a data point), a linear mixed-effect model will be selected instead of univariate general linear model repeated measures analysis. T Chi-square-test will be used for comparing the incident of AE between groups. The effect size to discriminate between groups will be estimated using Cohen's *d* effect size and represented as *d* in the results section. Values ranging from 0.20 to 0.49 indicate small; from 0.50 to 0.79 indicate medium, from 0.80 to 1.29 indicate large, and above 1.30 indicate very large effects. Values less than 0.20 are considered as having no noticeable effect. Spearman correlation of coefficient will be used to examine association between changes in motor parameters and changes in skin perfusion and plantar sensation post intervention. All analyses will be performed using SPSS statistics (version 24; IBM, Armonk, NY, USA) , with a significance level of  $p < 0.05$ .

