**Title: ELECTRICAL STIMULATION AS AN ADJUNCTIVE THERAPY TO ACCELERATE WOUND HEALING
IN PEOPLE WITH PERIPHERAL ARTERIAL DISEASE AND PLANTAR ULCERS & A RANDOMIZED
CONTROLLED TRIAL**

Identifier: NCT03821675

Date: 10/8/2021

Statistical analysis plan

Continuous data were reported with mean \pm standard deviation (SD). Categorical data were presented as count (%). Shapiro-Wilk test was conducted to identify the normal distribution of continuous variables. One-way ANOVA for normally distributed variables or Mann-Whitney U test for non-normally distributed variables was used to estimate differences of mean between control and intervention groups. χ^2 test was used to determine significant level between the groups for categorical variables. The effect size was measured using OR and 95% CI for categorical variables, and Cohen's d to discriminate the difference of primary and secondary outcomes between groups. Outcome changes were assessed over time compared to BL within (ie, time effect) and between (ie, time \times group effect) groups using linear mixed model for normally distributed outcome and generalized estimating equations for non-normally distributed outcome with adjustment for potential confounders. Least significant difference method was used for multiple pairwise comparisons. Pearson and Spearman correlation analysis were performed to assess the relationship between wound or demographics/clinical characteristics, and vascular outcomes. The level of statistical significance was set at $P < .050$. To detect changes in perfusion in individuals with marked limb ischemia, a sub-analysis of patients with moderate to severe peripheral arterial disease (PAD) (ABI < 0.8 or > 1.4 at BL)²⁴ was performed. To detect associated risk comorbidities influencing wound healing in those healers (defined as $\geq 50\%$ of area reduction)²⁵ vs non healers under E-stim, a sub-analysis in the IG was also performed.

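### Between-arm effects are tested as change from baseline, and neither document specifies the outcome's own baseline value (or baseline wound area) as a covariate; the test is valid but usually less precise than a baseline-adjusted one

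*SAP*

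**What the plan says.** **SAP.** The longitudinal analysis is described as "Outcome changes were assessed over time compared to BL within (ie, time effect"; the between-group comparison is the time-by-group effect. Normally distributed outcomes go to a linear mixed model and the others to GEE. Both are adjusted for potential confounders that are not listed. A separate between-group test (one-way ANOVA or Mann-Whitney) names no covariates.

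**Protocol, Statistical analysis.** Repeated-measures ANOVA is for "examining the effect of intervention in each group after adjusting by age and BMI". A linear mixed-effect model replaces it so that a missing data point does not remove a whole subject. No baseline outcome value is named.

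**Protocol, Study Design (Aim 2).** "Eligible participants will be randomized (ratio: 1:1"), with weekly visits for up to 4 weeks. The primary outcomes are changes in the speed of wound healing and in plantar sensation, the latter measured by vibratory perception threshold (VPT).

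**Protocol, Schedule of Events and Study Tasks.** Wound photos (which record wound size), VPT, the pain VAS, skin perfusion pressure (SPP) and the questionnaires are all taken at baseline and repeated later.

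**The concern.** When baseline is one of the repeated responses and each arm has its own free baseline mean, the week-4 time-by-group contrast is the difference between arms in mean change from baseline. Subtracting the baseline value fixes its coefficient at 1. Baseline adjustment estimates that coefficient and so usually leaves less residual variance. Main-effect terms for age and BMI do not recover the difference: they shift a subject's level at every visit and cancel out of the change.

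At stake is precision in a trial of about 18 to 20 per arm, using data that are already collected. A second consequence is that any chance difference between arms at baseline passes into the change-score estimate through regression to the mean.

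**Working it through.** **Inputs from the protocol (Sample size estimation).** Two-sided t-test, 80% power, "alpha level of 5% to observe a significant improvement in the intervention group", d = 1.35 taken from mobility in an earlier plantar-stimulation trial, and "18 subjects per group is required". Then: "Assuming a 10% drop out, the estimated sample size would be 20 subjects per arm".

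**Assumed inputs.** The correlation rho between baseline and week 4, and the SDs, are not in the documents. I take equal SDs (s) at both times and rho from 0.3 to 0.95.

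**1. The plan's own figure.** The dropout step reproduces: 18 / 0.90 = 20. The 18 does not. With d = 1.35, 80% power and two-sided 5%, a t-test needs 10 per group (9 by the normal approximation). That is a separate matter. Here it matters only that 18 per arm gives 97.6% power at d = 1.35, and 80% power at d = 0.961.

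**2. Does the SAP model have change-score precision?** One two-visit dataset with 18 per arm was simulated and fitted with time, group, time-by-group and an age-type covariate. The time-by-group estimate was 0.535 (SE 0.320). The plain difference in mean change was also 0.535 (SE 0.320).

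**3. Variance ratio.** Per subject:
- change score: 2(1 − rho)s²
- baseline-adjusted: (1 − rho²)s²
- ratio, adjusted to change: (1 + rho)/2

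Estimating the slope with N = 36 multiplies the adjusted variance by about 1 + 1/(N − 4) = 1 + 1/32 = 1.031.

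**4. Power.** Take an effect that has 80% power as a change score (d = 0.961). The adjusted standardised effect is 0.961 / √(ratio), with 33 degrees of freedom. The last column starts instead from d = 1.35 on the change scale, where the change score has 97.6% power.

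| rho | (1 + rho)/2 | with slope cost | power from 80% | power from 97.6% |
|---|---|---|---|---|
| 0.3 | 0.65 | 0.67 | 92.8% | 99.8% |
| 0.5 | 0.75 | 0.77 | 88.9% | 99.4% |
| 0.7 | 0.85 | 0.88 | 84.8% | 98.7% |
| 0.8 | 0.90 | 0.93 | 82.8% | 98.3% |
| 0.9 | 0.95 | 0.98 | 80.7% | 97.8% |
| 0.95 | 0.975 | 1.01 | 79.7% | 97.5% |

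Simulation (20,000 trials of 18 per arm at each rho) gave ratios of 0.66, 0.78, 0.88 and 0.98 at rho 0.3, 0.5, 0.7 and 0.9, in line with the slope-cost column. Break-even is where (1 + rho)/2 × 33/32 = 1, so rho = 64/33 − 1 = 0.94.

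**5. Chance imbalance.** At 20 per arm the SD of the baseline difference is √(2/20) = 0.316 SD, so a difference of at least 0.3 SD in either direction occurs in about 34% of trials. Given a difference of 0.3 SD, the change-score estimate shifts by (1 − rho) × 0.3: 0.15, 0.09 or 0.06 SD at rho 0.5, 0.7 or 0.8.

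**6. Where the formula does not apply.** Weekly healing speed has no baseline value of the same measure. Baseline wound area would be a prognostic covariate, reducing variance to about 1 − r² of the unadjusted value, where r is its unknown correlation with speed.

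**The case against.** A reader might infer that the baseline data are discarded. They are not: baseline is the reference for change and a response in the model. The SAP's open list of confounders could also include baseline values, so the documents show that these are not specified as covariates, not that they are excluded.

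A reader might also infer that the change-score test is biased. Over repeated randomisation it is not; the shifts in step 5 are conditional on the imbalance that occurred. The protocol's stated aim for this sample is modest too: to estimate a trend and to size a follow-up study.

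Nor is it safe to say that baseline adjustment always wins. That is a large-sample result. At 18 per arm the slope has to be estimated, the gain is under 1 point of power at rho 0.9, and the change score is slightly better above about 0.94. At the planned d = 1.35 there is little left to gain.

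All of this stands and limits the point to one of efficiency. Two things weigh on the other side. The 1.35 comes from mobility, not from wound healing or VPT, and the protocol concedes that the sample may not suffice for all its outcomes. The equal-SD assumption can also understate the gain: if the week-4 SD were 0.7 of the baseline SD with rho 0.7 (both assumed), the ratio before slope cost would be 0.2499 / 0.51 = 0.49.

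**Conclusion.** The point holds as a matter of efficiency, not validity. As written, the between-arm analysis has change-score precision, and the age and BMI terms do not alter that. For VPT, VAS, SPP and the questionnaires, under equal SDs and 18 per arm, baseline adjustment would bring the variance to about 0.77, 0.88 or 0.93 of its present value at rho 0.5, 0.7 or 0.8. That is worth roughly 9, 5 or 3 points of power for an effect now at 80%, and at most about 2 points if d = 1.35 holds. Because the documents give no correlation or SD, the actual size is unknown. These figures should not be carried over to weekly healing speed.

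**What to change.** In the protocol's Statistical analysis section and in the SAP, define the between-arm analysis in one of two ways:
- post-baseline values as the response, with that outcome's own visit-0 value as covariate: the same VPT site, and for SPP the reading before stimulation, since Aim 1 takes three readings around the one-hour session; or
- a mixed model that keeps baseline as a response but constrains both arms to a common baseline mean.

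For weekly healing speed, use baseline wound area as a prognostic covariate. Age and BMI may stay. Replace the open reference to confounders with the named list, fixed before arm codes are released. The SAP is written in the past tense, so if the codes are already released, report the adjusted result as a labelled sensitivity analysis. Keep change from baseline as description.

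The cost is SAP wording and a small change to the model code, with no new data or visits. The statistical downside is one degree of freedom and a trivial loss of precision if rho is very high.

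### Aim 2 is sized on one active-versus-sham t-test, but the SAP compares the arms by a time-by-group effect with unadjusted pairwise comparisons and names no deciding visit or contrast

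*SAP*

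**What the plan says.** **Sizing.** Protocol, Sample size estimation, bases the long-term aim on one comparison of active against sham, with "power of 80%, two –tailed t-test, and alpha level of 5" per cent. The effect size is a Cohen's d of 1.35, which "was observed for improvement of mobility post plantar electrical stimulation intervention" in an earlier trial. The result is that "18 subjects per group is required", and then: "Assuming a 10% drop out, the estimated sample size would be 20 subjects per arm".

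**Time of the question.** Protocol, Purpose, asks about benefit after four weeks of therapy. Protocol, Statistical analysis, describes "long term benefit (i.e. changes in primary and secondary outcomes after 4 weeks").

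**Analysis.** The SAP states: "Outcome changes were assessed over time compared to BL within (ie, time effect) and between" groups. The between-group part is a time-by-group effect from a linear mixed model, or from generalized estimating equations (GEE) when the outcome is not normal. It adds: "Least significant difference method was used for multiple pairwise comparisons". It does not say whether time is a category or a slope, which visit or contrast decides, or what covariance is used.

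**Visits.** The Schedule of Events marks wound photos at five visits and vibratory perception threshold (VPT) at three. Study Design, Aim 2, names healing speed and plantar sensation (measured by VPT) as the primary outcomes.

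**The concern.** A two-group t-test answers one question with one degree of freedom. A time-by-group effect with categorical time asks whether the arms differ in any pattern across visits. A significant result need not mean a benefit at week 4, and a week-4 benefit need not make the omnibus test significant. The sizing therefore does not describe the stated longitudinal test.

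The second risk is on the false-positive side. With pairwise comparisons unadjusted and no visit named, a report could rest an active-versus-sham claim on any visit that crosses 0.05. The unstated covariance adds to this, because the standard error of a week-4 contrast depends on it.

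**Working it through.** **Inputs from the documents:** 80% power, two-sided 5%, d = 1.35 (mobility), 18 evaluable per arm, 10% dropout, five wound-photo visits, three VPT visits. **Assumed, because the documents give no values:** shape of the effect over time, within-person correlation, and slope and residual SDs. Wound size at each photo visit is taken as the repeated wound measure.

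**1. The plan's own figure.** The normal approximation gives n per arm = 2(1.960 + 0.842)²/1.35² = 15.70/1.8225 = 8.6, so 9. The exact t calculation gives 10 (81% power). At 18 per arm the noncentrality is 1.35 × √(18/2) = 4.05 on 34 df, and power is 97.6%. So 18 per arm does not follow from d = 1.35 at 80%. The dropout step does reproduce: 18/0.90 = 20. The d that gives exactly 80% at 18 per arm is 0.96. That value is back-solved and appears nowhere in the documents. It is used below only to show what extra degrees of freedom cost.

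**2. Degrees of freedom.** The LSD step suggests categorical time. The interaction then has (2 − 1)(5 − 1) = 4 df for wound outcomes and (2 − 1)(3 − 1) = 2 df for VPT.

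**3. Power of the omnibus test at 18 per arm.** I used Hotelling's T² on changes from baseline, with noncentrality λ = (18/2) δ′V⁻¹δ, referred to F on (4, 31) or (2, 33) df. Covariances tried were compound symmetry and AR(1) with correlation 0.5 and 0.8, and random slopes. Worked cases for linear divergence at d = 0.961:
- Three visits: λ = 9 × 0.961² = 8.32, power 69%.
- Five visits, compound symmetry: λ = 1.25 × 8.32 = 10.40, power 66%.
- Five visits, AR(1) with correlation 0.8: λ = 8.32, power 55%.

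| Week-4 d | Shape of the difference | 4 df | 2 df |
|---|---|---|---|
| 0.96 | linear divergence | 55–66% | 69% |
| 0.96 | from week 1, plateau from week 2, or week 4 only | 74–100% | 82–100% |
| 1.35 | linear divergence (lowest case tried) | 87–94% | 94% |

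If time were instead a linear slope (1 df), power at d = 0.96 would be 80% for three visits and 59–88% for five.

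**4. Any-visit false positives.** I simulated no effect at 18 per arm on the log scale, with slope SD 0.05–0.20 per week and residual SD 0.15–0.20. The arms were compared unadjusted at each of four post-baseline visits. At least one p<0.05 occurs in about 11–16% of trials; a repeat run gave 10–15%. Four independent tests would give 1 − 0.95⁴ = 18.5%, and correlation between visits brings this down. The week-4 comparison alone rejects in 5%.

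**5. Covariance.** Under the same assumed SDs and no effect, a week-4 contrast from a random-intercept model rejects in about 9–24% of trials. With the week-4 change's own variance it rejects in about 5%.

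**The case against.** - **The SAP also contains 1-df tests.** It lists one-way ANOVA or Mann-Whitney between the arms, and with two arms one-way ANOVA is the t-test used for sizing. That is correct. But the sentence names no outcome and no visit, and Protocol, Statistical analysis, uses two-group tests of this kind for baseline comparison. If the sentence does cover outcomes, the SAP has two between-arm tests and no rule for which decides.
- **A reader might infer that the stated 80% drops to about 57% for wound outcomes and 70% for VPT.** The documents do not support this. Such figures need d = 0.96, which the documents do not contain, together with linear divergence. With other shapes the omnibus test can exceed 80%, so even the direction of the change is open. The 80% was stated for a mobility effect; no effect size or power is given for wound healing or VPT.
- **A reader might infer that a random-intercept model is planned and wrong.** Neither document specifies one. The supportable point is that the covariance is not stated; the 9–24% is conditional on that model and on assumed SDs.
- **LSD may be meant to follow only a significant interaction, or to compare times within an arm.** If it were gated by the omnibus test, the any-visit error with no effect at any visit could not exceed that test's 5%. The SAP states no such gate and does not say which pairs are compared.
- **The protocol concedes limited power.** It says the size may not suffice for every primary and secondary outcome. That tempers any complaint about power, but it does not settle which test decides.

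**Conclusion.** The concern holds as a gap in specification. The size rests on one t-test and the question is posed at 4 weeks. The SAP's longitudinal comparison is a time-by-group effect with unadjusted pairwise comparisons and no named visit, contrast or covariance. The firmest consequence is the freedom to choose a visit: about 11–16% false positives across four visits against a nominal 5%, under assumed variances and ungated comparisons.

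No single loss of power can be stated. It ranges from a clear loss (55–66% or 69%, at d = 0.96 with linear divergence) to little or none, and at the protocol's d of 1.35 power stays at 87% or more in every case tried. This is a worthwhile and cheap improvement rather than a fault that invalidates the trial. Separately, the stated 18 per arm is not what d = 1.35 requires.

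**What to change.** In the SAP, state that each primary outcome is decided by one 1-df contrast: the active-minus-sham difference in change from baseline at week 4. Take it from a linear mixed model with visit as a category, an unstructured covariance and Satterthwaite df. For wound healing, the change in wound size divided by 4 weeks is the mean weekly speed, so the same contrast serves. Where GEE replaces the mixed model, name the same contrast. Report the omnibus time-by-group effect and the earlier visits as supportive.

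The sample-size text should be re-derived for that contrast with an effect size for wound healing or VPT, or should say that none is available.

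The cost is wording only. The one downside is that a difference confined to weeks 1–3 becomes supportive. The SAP is written in the past tense; if outcome data had been seen before the contrast was fixed, the report should say so.

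### The SAP tests non-normal repeated outcomes by GEE with about 20 participants per arm and states no small-sample correction; with the usual robust Wald test the time × group test would exceed its 5% level, from slightly to about two-fold or more

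*SAP*

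**What the plan says.** The SAP states that a "Shapiro-Wilk test was conducted to identify the normal distribution of continuous variables". Changes from baseline, within and between groups, are then analysed by linear mixed model if the outcome is normal, and otherwise by "generalized estimating equations for non-normally distributed outcome with adjustment for potential confounders". The between-group effect is time × group, the significance level is 0.05, and pairwise comparisons use the least significant difference method.

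The SAP gives no GEE family, link, working correlation, covariance estimator, reference distribution or visit coding, and no small-sample adjustment. It names no outcome as non-normal. The Protocol (Statistical analysis) names repeated measures ANOVA and a linear mixed-effect model adjusted for age and BMI. It does not mention GEE, so it does not fill the gap.

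On size, the Protocol (Sample size estimation) says "The estimated number of study subjects is 40" and that "18 subjects per group is required", raised to 20 per arm for 10% dropout. The Schedule of Events has five time points for wound photos, three for vibratory perception threshold (VPT) and two for the vascular assessments.

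**The concern.** GEE inference is normally based on the sandwich variance and a chi-square reference. Both are large-sample results in the number of independent participants, not in the number of visits. With 18–20 participants per arm the sandwich is biased downward, and the chi-square reference ignores the error in estimating it. Both faults make the test reject too easily, and the excess grows with the number of interaction terms tested together.

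At stake is the between-group P value for any outcome sent to GEE. The primary outcomes are wound-healing speed and plantar sensation (Protocol, Study Design, Aim 2). Either might be sent there: wound area cannot fall below zero and reaches zero when a wound heals, and VPT is measured on a 0–50 V range in patients described as having moderate-to-severe neuropathy. The follow-up comparisons by least significant difference add no protection if the overall test is already liberal.

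**Working it through.** **Inputs.** Nominal level 0.05 (SAP). Participants per arm: 18 / 0.9 = 20, which reproduces the Protocol's dropout step. (The 18 does not follow from the cited d = 1.35, which needs about 10 per group by t-test. That is a separate matter; only the number of participants is used here.) If visits are coded as categories, the Schedule of Events gives time × group 4 df for wound photos, 2 df for VPT and 1 df for the vascular assessments.

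**Exact check for normal data.** Assume identity link, categorical visits, complete data, equal covariance in the arms and no covariates. GEE then compares the arms' mean change vectors. With n per arm, the sandwich variance is [(n−1)/n] × (S₁+S₂)/n, so the Wald statistic is W = T² × n/(n−1), where T² is the two-sample Hotelling statistic with ν = 2n−2. The test rejects when T² > χ²(q, 0.95) × (n−1)/n, and T² × (ν−q+1)/(νq) follows F(q, ν−q+1).

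| n per arm | q | χ² cut-off | T² cut-off | F cut-off | True level |
|---|---|---|---|---|---|
| 20 | 1 | 3.841 | 3.841 × 19/20 = 3.649 | 3.649 on (1, 38) | 6.4% |
| 20 | 2 | 5.991 | 5.991 × 19/20 = 5.692 | 5.692 × 37/76 = 2.771 on (2, 37) | 7.6% |
| 20 | 4 | 9.488 | 9.488 × 19/20 = 9.013 | 9.013 × 35/152 = 2.075 on (4, 35) | 10.5% |
| 18 | 4 | 9.488 | 9.488 × 17/18 = 8.961 | 8.961 × 31/136 = 2.042 on (4, 31) | 11.3% |
| 10 | 1 | 3.841 | 3.841 × 9/10 = 3.457 | 3.457 on (1, 18) | 7.9% |

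**Simulation for skewed data, 20 per arm, no true effect, uncorrected robust Wald test.** The identity-link cells used 40,000 runs, exchangeable correlation 0.7, and lognormal data with log-SD 0.5 or 1.0. The gamma-log cells used 1,500 runs, lognormal data with log-SD 0.8, and age and BMI as covariates.

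| Test | Normal, identity | Lognormal, identity | Lognormal, gamma-log |
|---|---|---|---|
| 1 df (two visits, or week-4 contrast) | 6.2–6.6% | 5.3–6.2% | 7.7% |
| 1 df, linear time over five visits | 6.5% | 5.5–6.1% | 9.9% |
| 2 df, three visits | 7.5% | 5.7–7.0% | 10.3% |
| 4 df, five visits | 10.4% | 7.7–9.6% | 19.1% |

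The normal column agrees with the exact results. With age and BMI as covariates and identity link, the 4-df test gave 11.2% (normal) and 8.5% (lognormal). At 18 per arm it gave 8.3–11.1% with identity link and no covariates, and 18.9% with gamma-log. Simulation error is about 0.1–0.15 percentage points in the 40,000-run cells and 0.6–1.0 in the 1,500-run cells.

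**After correction, 20 per arm.** With a bias-corrected sandwich and a t or F reference, the level was about 5% for normal data and about 2.5–5% for lognormal data with identity link. With gamma-log it was 5.3% (two visits), 6.5% (three visits), 7.7% (linear time) and 8.2% (joint, five visits). The correction removes the excess with identity link, but not fully with a log link.

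**The case against.** The strongest reply is that the SAP never says that an uncorrected sandwich was used. It is silent, and silence is not evidence that no correction was made. That is right, and the conclusion is conditional on it. But a reader of the SAP cannot tell whether a reported 5% is close to 5% or well above it.

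Four stronger readings are tempting, and the documents do not support them.

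- **That the test rejects twice as often as stated, whatever the outcome.** A factor near two needs a joint five-visit test or a log link, and the SAP specifies neither. Assessing change from baseline with pairwise comparisons is compatible with a joint test on categorical visits, but equally with 1-df contrasts, where identity link gives only 5–6.5%.
- **That wound area will go to GEE.** No outcome is named as non-normal. The primary outcome is speed of healing; a rate or change can take either sign, so the argument from raw area does not carry over directly.
- **That the inflation is extreme in the peripheral arterial disease (PAD) sub-analysis.** The 17–19% found for a joint 4-df test at 10 per arm does not apply. The SAP ties that sub-analysis to perfusion, which the Schedule of Events places at two visits, so the test has 1 df. No subgroup size is given, so 10 per arm is itself an assumption.
- **That this is the trial's one main between-group test.** The SAP also lists one-way ANOVA and Mann-Whitney comparisons and does not rank them.

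It can also be said that the Protocol (Sample size estimation) concedes that the trial may be too small for all outcomes and is meant to show trends and size a follow-up study. That lowers the stakes. It does not make a P value read at 0.05 correct.

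**Conclusion.** The concern holds in conditional form. If the SAP's GEE is run with the usual uncorrected robust variance and chi-square reference, the time × group test exceeds 5% in every case examined. At 20 per arm with identity link the true level is about 5–6.5% for 1 df, 6–7.5% for 2 df (three visits, as for VPT) and 8–10% for 4 df (five visits, as for wound photos). Gamma-log models reach about 19%. In the PAD perfusion sub-analysis (1 df) the level would be about 6.5–8% if there were 10 per arm.

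The assumptions are the robust covariance, the link and visit coding, the lognormal shapes and the within-person correlation; the documents give none of these. Whether any primary outcome is affected depends on Shapiro-Wilk results that the documents do not report. This is worth correcting because the remedy is cheap. It does not show that any particular result is false.

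**What to change.** Analyse all repeated outcomes with a linear mixed model, which the Protocol already names, using Satterthwaite or Kenward-Roger degrees of freedom. Where an outcome is skewed, use a transformed scale that can handle zero wound areas. Make the 1-df between-arm contrast at week 4 the test.

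If GEE is kept, state the family, link, working correlation and visit coding. Use a bias-corrected sandwich (Mancl-DeRouen or Kauermann-Carroll) with t or F reference distributions, preferably with identity link, since the correction does not fully restore 5% with a log link. A permutation test of the arm labels is an alternative. If a correction was in fact applied, one sentence naming it closes the point.

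The cost is a few lines of SAP text, slightly wider intervals and, since the SAP is written in the past tense, probably a re-run of the affected analyses. With strongly skewed data and identity link, the corrected GEE test can fall below 5% (about 2.5% at the lowest), which costs some power.
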